### 7.1. Analysis of demographics/baseline characteristics

The number of subjects enrolled into the study will be tabulated by study site and overall on the Total cohort.

The number of subjects enrolled per household will be tabulated by study site and overall on the Total cohort.

The numbers of withdrawn subjects will be tabulated according to the reason for withdrawal by study site, age category and overall on the Total cohort.

The distribution of the subjects in each cohort and reasons for exclusion will be tabulated by study site and overall.

- Minimum and maximum visit dates will be tabulated by study site and overall on the Total cohort.

Demographic characteristics (age at Visit 1 and gender) will be summarized using descriptive statistics by study site and overall on the Total cohort and on the ATP cohort.

Summary of history of dengue at Visit 1 will be summarized by study site and overall on the ATP cohort.

### 7.2. Description of ad-hoc visits

The analyses will be performed on the ATP cohort.

The distribution of ad-hoc visits with suspicion of dengue and ad-hoc visits without suspicion of dengue will be tabulated by study site, month and overall. Distribution of ad-hoc visits by month will also be displayed graphically by study site.

Ad-hoc visits without suspicion of dengue will be listed with the following characteristics: study site, ad-hoc visit date, subject number, age in year at ad-hoc visit, gender and diagnosis.

### 7.3. Characteristics of the suspected dengue cases

The analyses will be performed on the ATP cohort.

SDC will be listed with the following characteristics: study site, date of first visit for SDC, subject number, household number, dengue episode number, age at first symptom onset, gender, time interval between fever onset and first visit for SDC (in days), time interval between first symptoms onset and first visit for SDC (in days), early/late classification (based on interval between date of symptoms onset and date of first visit for SDC), date of blood sample, laboratory results at first visit for SDC, dengue classification (virologically confirmed, probable, other SDC), Dengue Virus Ab.IgG antibodies (ELISA) at Visit 1, hospitalization (Yes/No), at least 1 WHO 2009 warning signs (Yes/No), at least 1 WHO 2009 criteria for severe dengue (Yes/No) and most likely diagnosis (investigator opinion).

Distribution of suspected dengue cases type (early/late presenters) by month will be displayed graphically by study site and overall.

The following characteristics will be summarized for each category of dengue cases (Virologically, probable, other SDC):

- Temperature at first visit:  $<37.5$ ,  $\geq 37.5$ ,  $>38$ ,  $>38.5$ ,  $>39$ ,  $>39.5$ ,  $>40$
- Clinical symptoms at onset, from first and returned visits: frequency and proportion of cases with each symptom
- Final classification of the episode (hospitalisation (yes/no), at least one WHO 2009 warning signs (yes/no), at least one WHO 2009 criteria for severe dengue (yes/no), most likely diagnosis according to investigator opinion (dengue, chikungunya, influenza, malaria rotavirus or other enteric infection, other infection disease or non-infectious disease)).

### 7.4. Analysis of incidences

The analyses will be performed on the ATP cohort.

The following analyses will be performed by study site and overall:

- Incidence proportion of RT-qPCR confirmed symptomatic dengue infection during the study period.
- Incidence proportion of virologically confirmed symptomatic dengue infection during the study period.
- Incidence proportion of probable symptomatic dengue infection during the study period.
- Incidence proportion of virologically confirmed or probable symptomatic dengue infection during the study period.
- The numerator will be the number of subjects with at least one specified event reported during the study period. The denominator will be the number of subjects in the ATP cohort.

95% CI accounting for clustering effect will be computed on all estimated incidence proportions. The method for estimating the CIs is described in Section 12.1.

- The proportion, with 95%CI, of subjects with Dengue Virus Ab.IgG positive result (ELISA) at Visit 1 will be tabulated by study site and age category.

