## **10.7. Analysis of primary objective**

The primary analysis will be based on the ATP cohort. If the percentage of enrolled subjects with serological results excluded from the ATP cohort is 5% or more, a second analysis based on the Total cohort will be performed to complement the ATP analysis.

The following analyses will be performed:

Incidence rate of RT-qPCR confirmed symptomatic dengue infection with 95% CI: the numerator will be the number of subjects with RT-qPCR confirmed symptomatic dengue infection during the study period. The denominator will be the total person-years at risk, i.e., from enrolment until the first RT-qPCR confirmed symptomatic dengue infection during the entire study period.

CIs for incidence rates and prevalence will account for clustering of observations within households for the analyses by centre and also the stratification by centres for the overall analyses. Details of the methods will be described in the statistical analysis plan (SAP).

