## 2. STUDY DESIGN

### 2.1. Study design overview

[figure not shown]
- **Type of design:** Prospective, multi-country, multi-centre, household-based, cohort study/surveillance study.
- **Study population:** Subjects aged between 6 months and 50 years at the time of enrolment living in geographically-defined communities in Latin America and Southeast Asia. The study population comprised household members. The study population should have between 30% and 50% of adults (aged 18 years or above) per site
- **Recruitment:** The appropriate recruitment strategy was selected by each participating site. Two approaches have been considered: a school-based approach and a community-based approach without school involvement. The recruitment period should have preferably occurred outside the period of peak incidence of dengue, based on the local epidemiology of dengue in the past years.
- **Duration of longitudinal follow-up and number of visits:** The study duration was planned to be 24 months for each participating site. Subjects were planned to have a scheduled visit at enrolment, one visit at Month 12 and a conclusion visit at Month 24. The Month 12 and Month 24 visits may occur via a telephone contact for the Mexican site. The number of visits in case of febrile illness, referred as “suspected symptomatic dengue case”, varied by subject.
- **Type of study:** self-contained.
- **Data collection:** Electronic Case Report Form (eCRF).
- **Study termination:** in December 2017, GSK decided to deprioritise the development of the dengue purified inactivated vaccine (DPIV) candidate and to terminate the study EPI-DENGUE-007. This decision was made due to the scientific challenges and development risks associated with the candidate vaccine. Therefore, only two sites participated to the study, one in Mexico and one in Philippines. The site in Mexico conducted the study as planned per protocol Amendment 1. The site in Philippines conducted the study as per protocol Amendment 3 but the study was terminated at Visit 2 (Month 12). The planned sites in Malaysia and Thailand were not initiated before the decision of study termination was taken, so no subjects were enrolled in these countries. From the 1750 subjects planned to be enrolled in the study, only 850 subjects were finally enrolled in the study.

• Schematic representation of the scheduled visits – Mexico

The conclusion contact took place at Month 24 for the Mexico site

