## 3. OBJECTIVES

### 3.1. Primary objective

- To estimate the overall incidence rate of reverse-transcriptase quantitative polymerase chain reaction (RT-qPCR)-confirmed symptomatic DENV infection in a multi-centre cohort of household members aged 6 months to 50 years.

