## 10. CHANGES FROM PLANNED ANALYSES

The cohorts were clarified and the Total cohort without subjects with code 900 was added.

Due to study termination:

- Medical history and vaccination history for Japanese Encephalitis and Yellow Fever will not be summarised.
- Tertiary objectives will not be analysed.
- Refer to Section 7 for the laboratory tests performed. Those not performed will therefore not be analysed. In addition, no GMTs will be computed as only qualitative laboratory results (positive/negative) will be available.
- Incidence proportions will be computed instead of incidence rates for the primary and secondary objectives. Sub-analyses by season/year, by age category, gender, serotype and dengue serological status at the beginning of the analysis period will not be performed due to the low number of virologically confirmed or probable symptomatic dengue infection reported during the study period. In addition, analysis of incidences will only be performed on the ATP cohort.
- The proportion of subjects with Dengue Virus Ab.IgG positive result (ELISA) at Visit 1 will not be summarized among dengue cases (confirmed and probable) due to the low number of virologically confirmed or probable symptomatic dengue infection reported during the study period.
- The statistical methodology to estimate the CI for proportions accounting for clustering effect will not use stratification by center for the analyses on overall centers (refer to Section 12.1).

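### The primary objective is an overall incidence rate, but the SAP computes a pooled proportion over about 24 months of follow-up in Mexico and 12 in the Philippines

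*SAP*

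**What the plan says.** SAP 3.1 states the primary objective as "To estimate the overall incidence rate of reverse-transcriptase quantitative polymerase chain reaction (RT-qPCR)-confirmed symptomatic DENV infection". Protocol 10.7 fixes the estimator: the numerator is subjects with an RT-qPCR-confirmed case, and "The denominator will be the total person-years at risk", counted from enrolment to the first such case. Its confidence intervals allow for household clustering "and also the stratification by centres for the overall analyses".

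SAP 7.4 replaces this, by site and overall, with "Incidence proportion of RT-qPCR confirmed symptomatic dengue infection during the study period". The numerator is subjects with at least one event, and "The denominator will be the number of subjects in the ATP cohort". The virologically confirmed, probable and combined endpoints are treated the same way.

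SAP 10 lists the change under those due to study termination: "Incidence proportions will be computed instead of incidence rates for the primary and secondary objectives". It adds that the interval method "will not use stratification by center for the analyses on overall centers". Low case numbers are the reason given for dropping the sub-analyses and the seroprevalence among cases. No separate reason is given for dropping person-time.

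SAP 2.1 and the site table in SAP 7 show what the study period means at each site. Mexico covers Visits 1 to 3 and the 2017 and 2018 seasons. The Philippines stopped at Visit 2 (Month 12) and covers the 2018 season only.

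**The concern.** A proportion has meaning only over a stated risk period. Each site's proportion can be read as an approximate 24-month or 12-month risk. The pooled one mixes the two, so it is neither, and its value depends on how many subjects each site contributed.

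Two features add to this. A subject who withdraws before any event stays in the denominator as if followed throughout. The SAP 5.1 definition of the ATP cohort also omits the requirement in Protocol 10.3.2 for at least one follow-up contact, so a subject lost straight after enrolment counts in full.

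Termination is what made follow-up unequal. That strengthens the case for person-time and does not explain its removal. At stake is the headline figure, which cannot be set against the overall rates of 6.5 to 8.5 per 1000 person-years in Protocol Table 16, and the way the two site results read side by side. SAP 7.1 tabulates minimum and maximum visit dates and withdrawals, which bound follow-up but do not give person-years.

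**Working it through.** **1. The protocol's own figure.** Inputs from Protocol 10.2: 1750 subjects, 5% yearly dropout, 70% children at 8 and 30% adults at 5 per 1000 person-years, design effect 1.8.

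- Person-years: (1750 + 1662.5)/2 + (1662.5 + 1579.4)/2 = 3327 (stated 3327).
- Rate: 0.7 × 8 + 0.3 × 5 = 7.1 per 1000 (stated 7.1).
- Cases: 3327 × 0.0071 = 23.6 (stated about 24).
- Exact Poisson limits at 23.6 cases: 4.53 to 10.60 (stated 4.5; 10.6).
- Normal limits: 7.1 ± 1.96 × √(1.8 × 0.0071/3327) × 1000 = 3.26 to 10.94 (stated 3.3; 10.9).

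All reproduce, so the study was planned on person-time.

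**2. Person-time at the two sites.** Same formula, with enrolment from SAP 7:

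- Mexico: 350 × (0.975 + 0.95 × 0.975) = 665.4
- Philippines: 500 × 0.975 = 487.5
- Total: 1152.9, a mean of 1152.9/850 = 1.36 years per subject

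Mexico holds 350/850 = 41% of subjects but 665.4/1152.9 = 58% of person-time.

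**3. What the SAP's proportion would show.** Expected cases = rate × person-years; proportion = cases / subjects. Constant hazard is assumed. Actual cases and dropout are not in the documents, so this is illustration only. Rates are per 1000 person-years.

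| Rate, Mexico / Philippines | Proportion, Mexico | Proportion, Philippines | Pooled proportion | Pooled rate | Rate if follow-up were equal |
|---|---|---|---|---|---|
| 7.1 / 7.1 | 4.72/350 = 1.35% | 3.46/500 = 0.69% | 8.19/850 = 0.96% | 7.1 | 7.1 |
| 5 / 10 | 3.33/350 = 0.95% | 4.875/500 = 0.98% | 8.20/850 = 0.96% | 7.1 | 7.9 |
| 10 / 5 | 6.65/350 = 1.90% | 2.44/500 = 0.49% | 9.09/850 = 1.07% | 7.9 | 7.1 |

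The exponential form, 1 − exp(−rate × mean years), gives 1.34%, 0.69% and 0.96% in the first row. The pooled 9.6 per 1000 subjects is about 36% above 7.1 in number, because it is the rate times a mean follow-up of 1.36 years.

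**4. Range.** With a common rate from 6.5 to 8.5 and dropout from 0 to 10% a year: Mexico 1.17 to 1.70%, Philippines 0.62 to 0.85%, pooled 0.85 to 1.20%.

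**5. Seasons.** SAP 2.4 gives 1 July to 30 October in Mexico (122 days, 244 over two seasons) and 1 May to 30 November in the Philippines (214 days). Suppose the daily hazard were equal and confined to season, with every season-day observed. The proportions would then differ by 244/214 = 1.14 (1.11 with 5% dropout), while yearly rates would differ by 214/122 = 1.75. The side-by-side proportions would not show that difference.

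**6. Precision.** Eight cases in 1152.9 person-years is 6.9 per 1000, with exact Poisson limits of 3.0 to 13.7 before any allowance for clustering. The chance of no case at all, ignoring clustering, is exp(−4.72) = 0.9% in Mexico and exp(−3.46) = 3.1% in the Philippines at 7.1. At an assumed 1 to 2 per 1000 in Mexico it is 51% to 26%.

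**The case against.** The strongest reply is that this is a declared change in a terminated, descriptive study. SAP 10 states it, and Protocol 10.11 places the justification of changes in the final study report. SAP 7 tabulates the visits and seasons covered at each site, site results are planned beside the overall one, and no site comparison is planned. On that view the harm is one pooled number, and labelling its two windows would be enough. The illustrations also rest on chosen inputs. Constant hazard ignores the seasons. Rates of 5 and 10 lie outside the planned overall range. A common 7.1 may be too high for Mexico, because the Amendment 2 rationale in Protocol Appendix C calls incidence there too low to justify added blood draws. A pooled rate depends on site mix as well. Protocol 10.7 gives no censoring rule for event-free subjects, and routine surveillance contacts need no eCRF entry (Protocol Table 2).

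Much of this stands, and it limits the size of the point. The change is not concealed, a reader could rebuild approximate site rates, and with about eight expected cases no site contrast would be precise. The pooled rate is still shaped by the termination, as the table shows, so site rates must accompany it.

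It does not remove the point. Disclosure does not give the pooled proportion a risk period, and a descriptive estimate still needs a defined quantity. Few cases do not prevent a rate: the protocol planned an exact Poisson interval. Protocol 10.3.2 already ends surveillance at the last follow-up contact, so a stated censoring date completes the protocol's estimator. The absence of person-years is established for the SAP text only, because the table shells are in a separate document that was not available.

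**Conclusion.** The point holds. As written, the primary analysis does not estimate the primary objective, and its pooled figure has no defined time window. The documents alone establish this. The size depends on assumptions: under the planning rate and dropout, equal site rates appear almost twofold apart, and a twofold difference in the opposite direction almost disappears. Season-limited risk changes those contrasts but does not supply a common window. It should be fixed, with the expectation that the resulting rate will be imprecise.

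**What to change.** Amend SAP 7.4 and 10 as follows.

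- **Primary estimate.** Subjects with a first RT-qPCR-confirmed case per 1000 person-years, by site and overall. Person-time runs from enrolment to first event, withdrawal, or last visit or contact documented in the eCRF, using the days/365.25 rule already in SAP 12.4.3. Write the censoring date into the SAP.
- **Presentation.** Report person-years by site and show both site rates beside the pooled rate. State that the pooled rate is weighted by person-time (about 58% Mexico under the planning assumptions) and is not corrected for season.
- **Intervals.** Allow for household clustering and, overall, for stratification by centre as in Protocol 10.7. Fix a method for small and zero counts in advance, because SAP 12.1 gives no interval at zero cases. The choice is for the sponsor's statistician. These interval points are secondary, and the change of denominator does not depend on them.
- **Proportions.** Keep them only as a supplement over a common window, such as 12 months at both sites.
- **Fallback.** If person-time cannot be derived, give that as the reason in SAP 10 and label the overall figure with its two windows.

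The cost is SAP text, one table shell, some programming, and a check that censoring dates can be derived. Scheduled visits and withdrawals are in the eCRF. No new data collection is needed.

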**7.5. Analysis of tertiary objectives**

- Tertiary objectives will not be analysed.

**7.6. Analysis of serious adverse events**

Serious adverse events related to study procedures reported during the study period will be listed.

**8. ANALYSIS INTERPRETATION**

All analyses are descriptive.

**9. CONDUCT OF ANALYSES**

**9.1. Sequence of analyses**

The final analysis will be performed when all data have been collected and cleaned.

Study progress reports were generated during the study conduct to follow study progress using specified tables and using the study database as source data.

Description	Analysis ID	Disclosure Purpose (CTRS=public posting, SR=study report, internal)	Dry run review needed (Y/N)	Study Headline Summary (SHS) requiring expedited communication to upper management (Yes/No)	Reference for TFL
Final analysis	E1_01	SR, CTRS	No	No	Refer to EPI-DENGUE-007 BOD (200318) TFL (24-MAY-2019) DRAFT.docx
Study progress reports	E1_02	Monitoring	No	No	Refer to EPI-DENGUE-007 BOD (200318) Additional Analysis Request E01_02 Study Progress Report.docx

**9.2. Statistical considerations for interim analyses**

No interim analyses were planned.

## 10. CHANGES FROM PLANNED ANALYSES

The cohorts were clarified and the Total cohort without subjects with code 900 was added.

Due to study termination:

- Medical history and vaccination history for Japanese Encephalitis and Yellow Fever will not be summarised.
- Tertiary objectives will not be analysed.
- Refer to Section 7 for the laboratory tests performed. Those not performed will therefore not be analysed. In addition, no GMTs will be computed as only qualitative laboratory results (positive/negative) will be available.
- Incidence proportions will be computed instead of incidence rates for the primary and secondary objectives. Sub-analyses by season/year, by age category, gender, serotype and dengue serological status at the beginning of the analysis period will not be performed due to the low number of virologically confirmed or probable symptomatic dengue infection reported during the study period. In addition, analysis of incidences will only be performed on the ATP cohort.
- The proportion of subjects with Dengue Virus Ab.IgG positive result (ELISA) at Visit 1 will not be summarized among dengue cases (confirmed and probable) due to the low number of virologically confirmed or probable symptomatic dengue infection reported during the study period.
- The statistical methodology to estimate the CI for proportions accounting for clustering effect will not use stratification by center for the analyses on overall centers (refer to Section 12.1).

## 11. LIST OF FINAL REPORT TABLES, LISTINGS AND FIGURES

Refer to the document entitled EPI-DENGUE-007 BOD (200318) TFL (24-MAY-2019) DRAFT.docx.

The following group names will be used for the statistical analyses.

- Age categories:

Group order in tables	Group label in tables	Group definition for footnote
1	6 months-<12 months	From the 6th month birthday up to and including the day before the 1st year birthday
2	1-4 years	From the 1st year birthday up to and including the day before the 5th year birthday
3	5-8 years	From the 5th year birthday up to and including the day before the 9th year birthday
4	9-17 years	From the 9th year birthday up to and including the day before the 18th year birthday
5	18-50 years	From the 18th year birthday up to and including the day before the 51th year birthday

- Study sites (named center in the database):

Group order in tables	Group label in tables	Group definition for footnote
1	Mexico	No footnote
2	Philippines	

- Ad-hoc visits:

Group order in tables	Group label in tables	Group definition for footnote
1	Non SDC	Ad-hoc visits without suspicion of dengue
2	SDC	Ad-hoc visits with suspicion of dengue

- Symptomatic dengue confirmation status:

Group order in tables	Group label in tables	Group definition for footnote
1	Virologically confirmed	Symptomatic dengue cases confirmed by RT-qPCR or NS1
2	Probable	Probable symptomatic dengue cases
3	Other SDC	Symptomatic dengue cases not classified as virologically confirmed or probable

- Early/late presenter classification:

Group order in tables	Group label in tables	Group definition for footnote
1	Early presenter	Suspected dengue cases presenting at the health care facility within 5 days of symptoms onset
2	Late presenter	Suspected dengue cases presenting at the health care facility 6 days or more after symptoms onset

## 12. DATA DERIVATION RULE AND STATISTICAL METHODS

### 12.1. Methodology for computing CI

All confidence intervals (CIs) will be two-sided 95% CI.

This study will use cluster sampling (i.e. households within centers), inducing a potential clustering effect of the households and/or centers.

Individuals within a household are expected to have a more similar risk of infection compared to individuals from different households. For example, individuals living in the same household are more likely to share similar risk of being exposed to DENV infected mosquitoes. Similarly, subjects within a center may have a more similar risk of infection compared to individuals from different centers.

Therefore, CIs for proportions will account for clustering of observations. The 95% CIs will be based on generalized estimating equations (GEE) logistic regression model with robust variance estimate [Liang, 1986]:

- For an analysis by center, households will be considered as the clusters in the model.
- For an analysis on overall centers, the model with the highest estimated design effect (DE) among those using either households or centers as clusters will be used.
- SAS code:

```
PROC GENMOD DATA=xxx descending;
  CLASS cluster;
  MODEL event = / dist=bin link=logit;
  REPEATED subject= cluster / type=exch;
RUN;
```

Note that if the DE estimated from the selected GEE model is less than 1, then the classical logistic regression model will be used (GENMOD without cluster statement).

The design effect (DE), assessing the impact of clustered data on the variance of the estimated proportions (thus on the the precision of the estimated proportions), will be estimated as follows:

$$DE = \frac{\text{estimated variance accounting for the cluster sampling from GEE model}}{\text{variance estimated under the assumption of simple random sampling}}$$

If the proportion is 0% or 100%, or if all subjects used to compute the proportion are from the same cluster, then ICC, DE and 95%CI will not be estimated.

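### The highest-design-effect rule in SAP 12.1 can rest the overall 95% CI on two clusters, making it too wide for these two sites whenever they differ

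*SAP*

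**What the plan says.** Protocol 10.7 plans CIs that allow for household clustering and "also the stratification by centres for the overall analyses"; Protocol 10.8 and 10.10 repeat this. SAP 10 declares that the method "will not use stratification by center for the analyses on overall centers". SAP 12.1 sets out the replacement, an intercept-only logistic GEE with exchangeable correlation and robust variance. By-centre analyses use households as clusters. For overall analyses, "the model with the highest estimated design effect (DE) among those using either households or centers as clusters will be used". The reason offered is that "subjects within a center may have a more similar risk of infection compared to individuals from different centers".

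There are two guards. First, "if the DE estimated from the selected GEE model is less than 1, then the classical logistic regression model will be used". Second, no CI is computed when the proportion is 0% or 100%, or when all subjects fall in one cluster. No minimum number of clusters is set, and no small-sample correction.

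SAP 2.1 records that "only two sites participated to the study, one in Mexico and one in Philippines". The SAP is dated May 2019 and the termination decision December 2017, so the number of centres was known when the rule was written. SAP 7.4 applies the method to the primary estimate: "The following analyses will be performed by study site and overall". It defines a crude proportion: "The denominator will be the number of subjects in the ATP cohort".

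**The concern.** A robust variance is estimated from the spread between clusters. With two clusters there is one contrast, the gap between the two sites, and neither guard stops such a model being used. Taking the larger design effect means the two-cluster estimate is discarded when the gap happens to be small and kept when it is large.

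The planned stratification removes the between-site gap from the variance; the replacement can make that gap the whole of it. Shared risk within a centre is a fair observation, but it does not make a between-centre variance estimable from two centres.

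This interval accompanies the primary overall estimate. The study is descriptive, so the CI is its statement of precision, and Protocol 1.2 intends the results to inform future trials.

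**Working it through.** **1. The plan's own figures.** Protocol 10.2: D = 1 + (3 − 1) × 0.4 = 1.8. Person-years = (1750 + 1662.5)/2 + (1662.5 + 1579.4)/2 = 3327. Rate = 0.7 × 8 + 0.3 × 5 = 7.1 per 1000, or 23.6 cases. CI = 7.1 ± 1.96 × √(1.8 × 23.6)/3.327 = 3.3 to 10.9, as printed. The value 1.8 is used below as the household design effect.

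**2. Two-cluster variance.** Let the GEE weight the sites v₁ and v₂ (sum 1), so that μ = v₁p₁ + v₂p₂. Then p₁ − μ = v₂(p₁ − p₂) and p₂ − μ = −v₁(p₁ − p₂), and the sandwich is

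var(μ) = v₁²(p₁ − μ)² + v₂²(p₂ − μ)² = 2(v₁v₂)²(p₁ − p₂)².

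No separate within-site term appears. With weights proportional to 350 and 500, 2(v₁v₂)² = 0.1173, so the centre design effect is about 850 × 0.1173 × (1/350 + 1/500) × Z² = 0.48 Z², where Z is the ordinary two-site difference statistic. The centre model overtakes a household design effect of 1 at |Z| ≈ 1.44, and of 1.8 at |Z| ≈ √(1.8/0.484) = 1.93.

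**3. One case by hand: 0/350 and 12/500 (assumed counts).**
- Household CI: p = 12/850 = 1.41%; logit SE = √(1.8/(850 × 0.01412 × 0.98588)) = 0.390; CI 0.66–2.98%.
- Centre CI: the exchangeable fit gives weights 0.479 and 0.521, μ = 1.25%, var = 2 × (0.479 × 0.521)² × 0.024² = 7.17 × 10⁻⁵, logit SE = 0.00847/(0.0125 × 0.9875) = 0.686; CI 0.33–4.63%.
- Design effect: 5.6 on the logit scale, 4.4 on the proportion scale. Both exceed 1.8, so the centre model is used.

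**4. Other splits, against household design effect 1.8.**

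| Mexico + Philippines | Centre DE (logit) | Centre CI | Width ratio |
|---|---|---|---|
| 0 + 12 | 5.57 | 0.33–4.63% | 1.85 |
| 1 + 11 | 3.23 | 0.47–3.56% | 1.33 |
| 2 + 10 | 1.60 | household model used | – |
| 8 + 4 | 1.54 | household model used | – |
| 10 + 2 | 3.68 | 0.53–4.57% | 1.74 |
| 12 + 0 | 6.37 | 0.40–6.71% | 2.7 |

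With no household clustering the 0 + 12 ratio is 2.6. The centre interval is also built around a site-reweighted value: at 2 + 20 it is 2.35%, against a crude 22/850 = 2.59%.

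**5. Simulation.** Beta-binomial households of 2–4, 4000 runs per cell; the SAP rule against household-only GEE, both with the fallback to ordinary logistic regression when the design effect is below 1. Widths are medians in percentage points; coverage is of the fixed two-site mix.

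| Risk, Mexico/Philippines | ICC 0.1: rule v household | ICC 0.4: rule v household |
|---|---|---|
| 1.0%/1.0% | 1.60 v 1.54; coverage 96.8% v 96.4% | 2.05 v 1.98; 93.9% v 93.2% |
| 1.35%/0.7% (about equal annual rates) | 1.64 v 1.53 | 2.05 v 1.93 |
| 0.5%/1.5% | +11% | +8% |
| 0.4%/2% | 2.48 v 1.78; 98.6% v 96.1% | 2.73 v 2.22; 97.1% v 94.2% |
| 2%/0.4% | 2.56 v 1.60 | 2.58 v 2.02 |
| 0.2%/3% (extreme) | 4.67 v 2.06 | 4.67 v 2.55 |

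At 0.4%/2% the centre model is chosen in 73% (ICC 0.1) and 65% (ICC 0.4) of runs. A separately coded simulation at 0.5%/3%, compared with the centre-stratified CI, chose it in 94% (ICC 0) and 81% (ICC 0.4), with coverage of 99.7% and 97.9% against 95.2% and 93.8%.

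**6. Centres as a random sample.** Mean risk 1.3%, between-centre SD 0.4, 0.8 and 1.2 points: the SAP rule covers 92%, 83–86% and 74–81%; household-only covers 90–91%, 78–82% and 64–74%.

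**7. Visit 1 IgG, if an overall figure is reported.** Assumed 70% v 80%: 67.6–81.4% against 71.8–79.5% (1.8 times as wide). 60% v 80%: 54.7–81.9% against 67.5–75.6% (3.4 times). At 75% v 80% the household model is used.

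**The case against.** The strongest reply is that the rule is deliberately conservative, and that too wide presumes a target no section states. Protocol 10.7 names a variance method, not an estimand, while SAP 12.1 describes clustering by household and/or centre. On a random-centre reading the SAP rule covers better than households alone (step 6). That ranking stands. But the rule still falls to 74–81% there, because two clusters with a multiplier of 1.96 cannot deliver 95%. It meets neither target.

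Second, 12 cases may be too many. Applying 7.1 per 1000 to 350 subjects for two years and 500 for one, with 5% annual dropout, gives 0.975 × (350 + 332.5 + 500) = 1153 person-years and about 8 cases; SAP 10 itself cites few cases. With 8 cases the ratios are 1.43 (0 + 8), 1.54 (7 + 1) and 2.15 (8 + 0), and at 1 + 7 the household model is used. The effect is smaller but does not vanish.

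Third, the observed gap is noisy, so its expected square does include within-site sampling error. That is correct: the estimate is unstable rather than wholly blind to it.

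Fourth, the IgG bullet in SAP 7.4 names site and age category only. An overall IgG interval follows only from that section's lead-in and the objective in SAP 3.2, so the IgG figures are conditional.

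**Conclusion.** The concern holds. SAP 12.1 allows a two-cluster CI for the primary overall proportion, and nothing in it prevents one. For the two sites as fixed strata, the target inferred from the protocol's stratification, that CI is too wide when the sites differ.

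The size depends on a gap the documents do not give. Two seasons in Mexico against one in the Philippines (SAP 7) would raise the Mexican cumulative proportion; the low incidence noted for the Mexican site in the Amendment 2 rationale (Protocol Appendix C) would lower it. Neither direction nor size is known. The excess is 6–7% at about equal annual rates and about 1.2 to 1.6 times at 0.4% v 2% in either direction; it is larger for one-sided case splits. Reported proportions and by-site CIs are unaffected. It should be fixed because it concerns the primary interval and the change is small.

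**What to change.** In SAP 12.1, delete the highest-design-effect rule and the centre-as-cluster model. For every overall CI use the household-clustered GEE already specified by centre, and keep the fallback for a design effect below 1. Form the cluster identifier from centre and household together, because Protocol 7.2 numbers households sequentially at each site and numbers may repeat. State that the overall CI describes the two participating sites and does not extend to other centres.

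Centre may be kept as a stratum where both sites have cases; widths are almost the same, so this is optional.

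The cost is a few words and one model fewer; no new data. There are two downsides. At household ICC 0.4 with few cases, coverage was 93.2–94.9% (92.4–92.9% for a stratified version). And a reader who takes the interval to cover centres in general would be further misled than under the SAP rule, so the statement of target is needed.
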